VP-VSJ-110-2101

**A SINGLE-CENTER, DOUBLE-MASKED, RANDOMIZED,
PLACEBO-CONTROLLED, PHASE 2, EVALUATION OF THE
SAFETY AND EFFICACY OF VSJ-110 OPHTHALMIC
SOLUTION IN THE TREATMENT OF ALLERGIC
CONJUNCTIVITIS USING AN ALLERGEN CHALLENGE
MODEL**

Authors:

[REDACTED]

Clinical Study Protocol

Sponsor:

Vanda Pharmaceuticals Inc.
[name]
[name]
[name]
USA

Study Product:

VSJ-110 0.034% Ophthalmic Solution

Protocol Number:

VP-VSJ-110-2101

Study Phase:

II

IND Number:

148258

Date: 10 November 2020

Status: Amendment 1.0 Final

Number of Pages: 81

CONFIDENTIAL

This document is confidential and the property of Vanda Pharmaceuticals Inc. No part of it may be transmitted, reproduced, published, or used by other persons without prior written authorization from the study sponsor.

VP-VSJ-110-2101

Confidential

Vanda Pharmaceuticals Inc.

SYNOPSIS

Name of Sponsor/Company: Vanda Pharmaceuticals Inc.	
Name of Investigational Product: VSJ-110 0.034%	
Title of Study: A Single-Center, Double-Masked, Randomized, Placebo-Controlled, Phase 2, Evaluation of the Safety and Efficacy of VSJ-110 Ophthalmic Solution in the Treatment of Allergic Conjunctivitis Using an Allergen Challenge Model	
Study Center(s): Single-center in the United States	
Studied Period: Date first patient enrolled: October 2020 Estimated study duration: 3 months	Phase of Development: II
Number of Patients (planned): Approximately 40 patients randomized (20 per arm, 1:1 randomization scheme) who have a positive history of ocular allergies. Discontinued subjects will not be replaced (i.e., their subject numbers will not be reassigned/reused).	
Inclusion Criteria 
Each subject must:
 
 1) be at least 18 years of age at Visit 1 of either gender and any race; 2) provide written informed consent and sign the HIPAA form; 3) be willing and able to follow all instructions and attend all study visits; 4) have a positive history of ocular allergies and a positive skin test reaction to a seasonal (grass, ragweed, and/or tree pollen) or perennial allergen (cat dander, dog dander, dust mites, cockroach) as confirmed by an allergic skin test conducted at Visit 1 or within the last 24 months; 5) be able and willing to avoid all disallowed medications for the appropriate washout period and during the study (see exclusion 6); 6) be able and willing to discontinue wearing contact lenses for at least 72 hours prior to and during the study trial period; 7) (for females capable of becoming pregnant) agree to have urine pregnancy testing performed at screening (must be negative), prior to dosing with investigational product, and exit visit; must not be lactating; and must agree to use a medically acceptable form of birth control¹ throughout the study duration. Women considered capable of becoming pregnant include all females who have experienced menarche and have not 	

¹Acceptable forms of birth control are spermicide with barrier, oral contraceptive, injectable or implantable method of contraception, transdermal contraceptive, intrauterine device, or surgical sterilization of partner. For non-sexually active females, abstinence will be considered an acceptable form of birth control.

VP-VSJ-110-2101

Confidential

Vanda Pharmaceuticals Inc.

experienced menopause (as defined by amenorrhea for greater than 12 consecutive months) or have not undergone successful surgical sterilization (hysterectomy, bilateral tubal ligation, or bilateral oophorectomy);

- 8) have a calculated best-corrected visual acuity of 0.7 logMAR or better in each eye as measured using an ETDRS chart;
- 9) have a positive bilateral post-CAC reaction (defined as having scores of ≥ 2 ocular itching and ≥ 2 conjunctival redness) within 10 (± 2) minutes of instillation of the last titration of allergen at Visit 2;
- 10) have a positive bilateral post-CAC reaction (defined as having scores of ≥ 2 ocular itching and ≥ 2 conjunctival redness) for at least two out of the first three time points² following the challenge at Visit 3.

Exclusion Criteria

Each subject must not:

- 1) have known contraindications or sensitivities to the use of the investigational product or any of its components;
- 2) have any ocular condition that, in the opinion of the investigator, could affect the subject's safety or trial parameters (including but not limited to narrow angle glaucoma, clinically significant blepharitis, follicular conjunctivitis, iritis, pterygium, history of corneal transplantation or a diagnosis of dry eye);
- 3) have had ocular surgical intervention within three (3) months prior to Visit 1 or during the study and/or a history of refractive surgery within the past six (6) months;
- 4) have a known history of retinal detachment, diabetic retinopathy, or active retinal disease;
- 5) have the presence of an active ocular infection (bacterial, viral or fungal) or positive history of an ocular herpetic infection at any visit;
- 6) use any of the following disallowed medications during the period indicated **prior to Visit 2** and during the study:

7 Days

- systemic or ocular H₁ antihistamine, H₁ antihistamine/mast cell stabilizers, H₁ antihistamine- vasoconstrictor drug combinations;
- decongestants;
- monoamine oxidase inhibitors;
- all other topical ophthalmic preparations (including artificial tears);
- lid scrubs;
- topical prostaglandins or prostaglandin derivatives;
- ocular, topical, or systemic nonsteroidal anti-inflammatory drugs (NSAIDs);

14 Days

² not necessarily at the same time point

VP-VSJ-110-2101

Confidential

Vanda Pharmaceuticals Inc.

- inhaled, ocular, topical, or systemic corticosteroids or mast cell stabilizers;

45 Days

- depo-corticosteroids;

Note: Currently marketed over-the-counter anti-allergy eye drops (i.e. anti-histamine/ vasoconstrictor combination products such as Visine®-A®) may be administered to subjects by trained study personnel at the end of Visits 2, 3, 4b, 5b and 6, after all evaluations are completed.

- 7) have any significant illness (e.g. any autoimmune disease requiring therapy, severe cardiovascular disease [including arrhythmias] the investigator feels could be expected to interfere with the subject's health or with the study parameters and/or put the subject at any unnecessary risk (includes but is not limited to: poorly controlled hypertension or poorly controlled diabetes, a history of status asthmaticus, organ transplants, a known history of persistent moderate or severe asthma, or a known history of moderate to severe allergic asthmatic reactions to any of the study allergens);
- 8) have received allergy immunotherapy within the last 2 years;
- 9) manifest signs or symptoms of clinically active allergic conjunctivitis in either eye at the start of Visits 2, 3 or 4a (defined as the presence of any itching or >1 [greater than 1] redness in any vessel bed);
- 10) have a history of glaucoma or ocular hypertension;
- 11) have planned surgery (ocular or systemic) during the trial period or within 30 days after;
- 12) have used an investigational drug or medical device within 30 days of the study or be concurrently enrolled in another investigational product trial;
- 13) be a female who is currently pregnant, planning a pregnancy, or lactating;
- 14) have symptoms that, in the opinion of the investigator, may be associated with COVID-19 or in the last 14 days came into contact with someone diagnosed with COVID-19.

Investigational Product, Dosage, and Mode of Administration:

Topical ocular VSJ-110 0.034% will be administered bilaterally into the eye.

Duration of Treatment (Randomization Phase):

This study consists of seven (7) office visits over a period of up to eleven (11) weeks.

Reference Therapy, Dosage, and Mode of Administration:

Topical ocular Vehicle of VSJ-110 will be administered bilaterally into the eye.

Objectives:

Primary Objective:

- To evaluate the efficacy of VSJ-110 0.034% compared to vehicle for the treatment of the signs and symptoms of allergic conjunctivitis.

Pharmacogenomic Sub-Study:

- To identify genetic markers associated with allergic conjunctivitis and/or response to VSJ-110

VP-VSJ-110-2101

Confidential

Vanda Pharmaceuticals Inc.

Overall Design:

Duration: This study consists of seven (7) office visits over a period of up to eleven (11) weeks.

Screening Period: At Visit 1, subjects will sign the informed consent and an allergic skin test will be performed, if required. At Visit 2, each qualifying subject will undergo a bilateral conjunctival allergen challenge (Ora-CAC[®]) titration using an allergen they had a positive reaction to on their skin test. Subjects who elicit a positive reaction post-CAC will undergo the confirmation CAC at Visit 3 using the same allergen they qualified with at Visit 2.

Treatment Period: Treatment will begin at Visit 4a after subjects are randomized. At this visit, subjects will receive an in-office dose of the treatment they were randomized to receive. Approximately 16 hours post-instillation of study medication, subjects will undergo CAC at Visit 4b. At Visit 5a, subjects will receive an in-office dose of the same study medication. Approximately 8 hours post-instillation of study medication, subjects will undergo CAC at Visit 5b. At Visit 6, subjects will receive an in-office dose of the same study medication approximately 15 minutes prior to CAC. Subjects will receive a final in-office dose of the same study medication at Visit 7 prior to Schirmer's Test and Optical Coherence Tomography (OCT).

Criteria for Evaluation:

Efficacy Measures:

Primary:

- Ocular itching evaluated by the subject at 3(± 1), 5(± 1), and 7(± 1) minutes post-CAC (0-4 scale, allowing half unit increments) at Visits 4b, 5b, and 6.
- Conjunctival redness evaluated by the investigator at 7(± 1), 15(± 1), and 20(± 1) minutes post-CAC (0 to 4 scale) at Visits 4b, 5b, and 6.

Secondary:

The following assessments will occur at 7(± 1), 15(± 1), and 20(± 1) minutes post-CAC (all use a 0 to 4 scale, except eyelid swelling, 0 to 3) at Visits 4b, 5b, and 6:

- Ciliary redness evaluated by the investigator
- Episcleral redness evaluated by the investigator
- Chemosis evaluated by the investigator
- Eyelid swelling evaluated by the subject
- Tearing evaluated by the subject
- Rhinorrhea, nasal pruritus, ear or palate pruritus, and nasal congestion evaluated by the subject

VP-VSJ-110-2101

Confidential

Vanda Pharmaceuticals Inc.

Exploratory:

- Digital Photographs may be taken of all subjects within 10 minutes of the last post-CAC assessment at Visits 3, 4b, 5b, 6.
- Tear meniscus quantitation & replenishment dynamics: Schirmer's Test and OCT at Visit 7.
- Buccal cell samples will be collected at Visit 1 for pharmacogenetic assessments.
- Pharmacokinetic Measures at pre-dose and 5 minutes(± 2), 15 minutes(± 2), and 30 minutes(± 2) post dose at Visit 4a.

Safety Measures:

- Adverse Events assessed at all office visits
- Visual Acuity at Distance Utilizing an ETDRS chart conducted at Visit 2, 3, 4a, 4b, 5a, 5b, 6, and 7.
- Slit lamp Biomicroscopy conducted at Visit 2, 3, 4a, 4b, 5a, 5b, 6, and 7.
- Intraocular Pressure measured at Visit 1 and Visit 7
- Dilated Fundoscopy measured at Visit 1 and Visit 7

Tolerability Measures:

- Drop comfort assessment (assessed by subjects upon instillation, at 1, and 2 minutes post-instillation) at Visit 4a. Drop descriptor query (assessed at 3 minutes post-instillation) at Visit 4a.

General Statistical Methods and Types of Analyses

For all the analyses, treatment group differences will be tested at a 2-sided significance level of 0.05. The primary statistical analysis will be based on ANOVA model. Categorical variables such as response will be evaluated using Cochran-Mantel-Haenszel (CMH) method or Fisher's exact test. The details of analysis methods will be specified in the SAP.

Summary of Known and Potential Risks and Benefits to Human SubjectsRefer to [Investigator's Brochure \(IB\)](#)

VP-VSJ-110-2101

Confidential

Vanda Pharmaceuticals Inc.

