20. STATISTICS

20.1. Number of Subjects (approximate)

Approximately 80 subjects will be screened in order to enroll approximately 40 subjects at one (1) site. Discontinued subjects will not be replaced (i.e., their subject numbers will not be reassigned/reused).

The sample size chosen for this study is not based solely on statistical considerations, but was chosen after taking into consideration existing data for approved treatments for AC and the preclinical profile of the drug candidate VSJ-110.

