20.2. Study Population Characteristics

Subjects at least 18 years of age, of either gender or any race, who have a positive history of allergic conjunctivitis, and who meet all of the inclusion criteria and none of the exclusion criteria.

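### Does enrolling only allergic subjects leave the pharmacogenomic objective without a comparison it needs?

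*Combined protocol and SAP*

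**What the plan says.** The Synopsis, under Objectives, sets a pharmacogenomic aim separate from the primary objective: "To identify genetic markers associated with allergic conjunctivitis and/or response to VSJ-110". The only matching procedure in the public text is one line among the exploratory measures: "Buccal cell samples will be collected at Visit 1 for pharmacogenetic assessments".

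Eligibility is restricted to affected people. Inclusion criterion 4 requires subjects to "have a positive history of ocular allergies and a positive skin test reaction to a seasonal" or perennial allergen. Criterion 9 adds a positive bilateral challenge at Visit 2. Criterion 10 requires another such reaction "for at least two out of the first three time points² following the challenge at Visit 3". Section 20.2 describes the population in the same way: subjects "who have a positive history of allergic conjunctivitis, and who meet all of the inclusion criteria and none of the exclusion criteria".

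The Synopsis gives the size as "Approximately 40 patients randomized (20 per arm, 1:1 randomization scheme) who have a positive history of ocular allergies", and section 20.1 adds the screening figure: "Approximately 80 subjects will be screened in order to enroll approximately 40 subjects at one (1) site". The control is vehicle: "Topical ocular Vehicle of VSJ-110 will be administered bilaterally into the eye".

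The Synopsis methods paragraph and section 20.3 leave analysis detail to the SAP. No genetic test, marker list, significance threshold or reference population appears in the public text, which passes from the Synopsis straight to section 20.

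**The concern.** A marker is associated with a disease when its frequency differs between people who have the disease and people who do not. Here every randomised subject is a case, and the vehicle arm is a control for treatment, not for disease. Read strictly, the first clause of the objective has no contrast behind it in the randomised set. That is a question of identifiability, which a larger trial of the same design would not cure.

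The worry is that a disease marker might later be reported against a comparison group picked after the data were seen, with differences in ancestry and genotyping left uncontrolled. A second worry is that markers of response might be sought in the active arm alone, where drug effect and natural reactivity cannot be told apart.

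**Working it through.** The documents give no power, effect size or marker count for the genetic work, so there is no figure of theirs to reproduce beyond 20 × 2 = 40 randomised. Allele frequencies, odds ratios, carrier shares, SD effects and marker counts below are assumptions.

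**1. Disease status among randomised subjects.** Criteria 4, 9 and 10 make it constant: about 40 affected and none unaffected. The contrast is not estimable within this set.

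**2. Who may be sampled.** Buccal cells are taken at Visit 1. The challenges that decide entry come at Visits 2 and 3, and the skin test, where needed, is itself done at Visit 1. Screened minus enrolled is 80 − 40 = about 40 people who may have given DNA without being randomised. They are not designed controls, since some will fail for reasons unrelated to allergy, and the text does not say whether their samples are kept or used. The randomised count therefore does not settle how many comparison samples exist.

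**3. The response clause.** This needs a marker-by-treatment interaction, which two randomised arms allow. Take a carrier share of one half, giving four cells of 10, and a common SD:

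- SE of the interaction = SD × √(4/10) = 0.632 SD
- SE of the marker main effect = SD × √(1/20 + 1/20) = 0.316 SD
- Power for an interaction of 0.8 SD ≈ Φ(0.8/0.632 − 1.96) = Φ(−0.69) ≈ 24% at two-sided 0.05

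The clause can be studied, though with little power.

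**4. What an unaffected group would add.** Suppose 40 unaffected controls, so n = 80 alleles per group, and an odds ratio of 2. With p0 and p1 the control and case allele frequencies, p̄ their mean and q = 1 − p throughout:

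power = Φ{[(p1 − p0) − z√(2p̄q̄/n)] / √[(p0q0 + p1q1)/n]}

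| p0 | p1 | Power at 0.05 | Power at 0.05/100 = 0.0005 | Subjects per group for 80% power at 0.05 |
|---|---|---|---|---|
| 0.1 | 0.182 | 32% | 2% | 142 |
| 0.2 | 0.333 | 48% | 6% | 86 |
| 0.3 | 0.462 | 56% | 8% | 71 |

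**5. What rewording to severity would add.** If untreated Visit 3 scores in the 40 were analysed as a quantitative trait, the correlation detectable with 80% power is r = tanh[(z + 0.842)/√(40 − 3)].

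- Two-sided 0.05: (1.960 + 0.842)/6.083 = 0.461, so r = 0.431 and r² = 0.185.
- Assumed genome-wide 5 × 10⁻⁸: 6.293/6.083 = 1.035, so r = 0.776 and r² = 0.602.

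One pre-named marker would have to explain about 18% of the variance, or about 60% under a genome-wide search. Comparing carriers with non-carriers for a 0.8 SD difference gives 53% to 72% power for carrier shares of 20% to 50% (7% to 17% at 0.0005).

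These figures assume an unselected, roughly normal trait. The Visit 3 scores are not that. Criterion 10 requires at least 2 for both itching and redness on scales running from 0 to 4, section 20.5.1 allows redness only whole numbers, and each subject is challenged with an allergen settled individually at the Visit 2 titration. The score is truncated and does not measure severity under a common stimulus.

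**The case for a change.** The strongest reply is that the first clause, on its ordinary reading, does need unaffected people, and none are named. Screen failures cannot be assumed to fill the role, because someone can fail on acuity or medication use, or fall short of the challenge threshold while truly allergic. If the sponsor means severity among allergic subjects, saying so would cost one sentence, and section 20.3 lets statistical methods be updated in the SAP before database lock without an amendment.

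Much of this stands. The randomised set has no disease-status contrast, vehicle does not supply one, and the public text names no comparator. A careful author could name an external reference or defined screen failures, or limit the clause to allergen reactivity with allowance for allergen, titrated level and the entry threshold.

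What does not stand is the step to an objective that cannot be met. The and/or wording is satisfied by markers of response alone. The clause can also be read to cover reactivity among affected subjects. An active-arm-only analysis is nowhere proposed. And since the public text omits what lies between the Synopsis and section 20, a sub-study section or named reference population cannot be ruled out.

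**Conclusion.** The observation about the randomised subjects is right: 40 cases and no unaffected group among them. It calls for no change. The gap is one of wording in an exploratory objective, with no stated genetic rule, test or number that would yield a wrong result. An analyst would fill it sensibly by using both arms for response and by making no disease-marker claim without a named reference.

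The gain from altering the plan would be small. With 40 added controls, power for an odds ratio of 2 would be 32% to 56% on one marker and 2% to 8% after correction for 100. The obvious substitute, Visit 3 severity, is weakened by the trial's own entry rule and individual titration. Efficacy and safety conclusions are unaffected either way.

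This rests on the assumed allele frequencies, effect sizes and marker counts above, and on the public text alone. It would need another look if a disease-marker claim were later made from randomised subjects without a defined comparison group.

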20.3. Statistical Methods and Analysis Plan

This section describes the planned statistical analyses in general terms. A complete description of the methodology will be specified in a statistical analysis plan (SAP). Any changes in the statistical methods described in this protocol that occur prior to database lock will be documented in the SAP and will not require a protocol amendment.

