20.4. Statistical Hypotheses and Methods of Analysis

Prior to Database lock a Statistical Analysis Plan will be finalized detailing the Efficacy, Safety, and Tolerability analyses that will be performed.

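### The primary model is named only as ANOVA and no baseline term is committed to; adjusting for the pre-randomisation Visit 3 score is an optional, modest efficiency gain

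*Combined protocol and SAP*

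**What the plan says.** The synopsis (General Statistical Methods and Types of Analyses) states that "The primary statistical analysis will be based on ANOVA model", tested two-sided at 0.05. It lists no covariate and adds that "The details of analysis methods will be specified in the SAP". Section 20.4 says: "Prior to Database lock a Statistical Analysis Plan will be finalized detailing the Efficacy, Safety, and Tolerability analyses that will be performed". The detailed SAP is not part of the text supplied.

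Sections 20.5.1 and 20.5.2 define the efficacy variables as post-challenge scores at Visits 4b, 5b and 6. They mention neither change from baseline nor a baseline term. Baseline appears in three places, never as a model term:
- section 20.4.1, where the Intent-to-Treat definition refers to a post-baseline measurement;
- section 20.4.3, for descriptive summaries;
- section 20.6, as an optional subgroup factor.

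A pre-treatment value of both primary measures nevertheless exists. Inclusion criterion 10 requires each subject to "have a positive bilateral post-CAC reaction", with itching and conjunctival redness both scored at least 2, at two or more of the first three time points "following the challenge at Visit 3". Visit 3 belongs to screening, and "Treatment will begin at Visit 4a after subjects are randomized".

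**The concern.** In a trial of about 40 subjects, precision is scarce. A score for the same measure, taken under the same kind of challenge before treatment, is a natural covariate. If it predicts the post-treatment score, a model with treatment alone leaves explainable variance in the error term.

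What is at stake is the precision of the treatment comparison, not its validity. There is also a smaller point of pre-specification. If an adjusted analysis is wanted later, the covariate, the way the eyes are combined and the Visit 3 time point should already be fixed, so that none of them is chosen after unmasking.

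**Working it through.** **Plan's own figure.** The planned size is about 40 subjects, 20 per arm (synopsis; section 20.1). No effect size, SD or power accompanies it, and section 20.1 says the size does not rest on statistical considerations alone. There is nothing to reproduce, so the comparison below uses an assumed effect.

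**Inputs.** From the documents: n = 20 per arm and two-sided alpha 0.05. Assumed: one subject-level score per test, a true difference d = 0.75 SD of that score, and an observed baseline-outcome correlation r, shown as a range.

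**ANOVA.** Noncentrality = d / sqrt(2/n) = 0.75 / sqrt(0.1) = 2.372, on 38 df. Power is 63.7%. The difference detectable with 80% power is 0.909 SD.

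**ANCOVA.** The variance is multiplied by (1 − r²) × (1 + 1/(2n − 4)) = (1 − r²) × (1 + 1/36), on 37 df. The second factor is the expected cost of chance baseline imbalance. For example, at r = 0.37 the multiplier is 0.8631 × 1.0278 = 0.887, the noncentrality is 0.75 / sqrt(0.0887) = 2.518, and power is 68.9%.

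| Observed r | Variance multiplier | Power at 0.75 SD | Change from ANOVA (points) | Detectable difference, 80% power |
|---|---|---|---|---|
| 0 | 1.028 | 62.5% | −1.2 | 0.922 SD |
| 0.16 | 1.001 | 63.6% | −0.1 | 0.910 SD |
| 0.20 | 0.987 | 64.3% | +0.5 | 0.904 SD |
| 0.30 | 0.935 | 66.6% | +2.8 | 0.880 SD |
| 0.37 | 0.887 | 68.9% | +5.1 | 0.857 SD |
| 0.50 | 0.771 | 74.9% | +11.1 | 0.799 SD |

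The two powers are equal at r = 0.169.

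**Which r is plausible?** The entry rule narrows the spread of Visit 3 scores, and the scales are coarse (half units for itching, whole units for redness). Both lower the observed correlation. I simulated a latent score, shifted the outcome by −0.2, rounded both to the scale steps, clipped them to 0–4 and required a baseline of at least 2. Means, SDs and underlying correlations are all assumptions.
- Latent mean 2.3, SD 0.7: an underlying 0.3 to 0.5 appears as 0.22 to 0.37 for itching and 0.20 to 0.35 for redness.
- Latent mean 2.0, SD 0.5 to 0.7: an underlying 0.3 appears as only 0.16 to 0.18 for redness, which is at break-even.

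A fair working range is therefore about 0.16 to 0.37, or a gain of about 0 to 5 points.

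**Larger effects.** At an assumed 1.2 SD, ANOVA power is already 95.9%. ANCOVA adds 0.2 points at r = 0.20 and 1.6 points at r = 0.37.

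**The case against.** The strongest reply is that this concerns a deferred detail and not a decision. The synopsis says only that the analysis is based on ANOVA, section 20.3 describes its own text as general, and covariates are the kind of detail that the SAP is there to settle. That stands. A reader might infer that the plan has rejected baseline adjustment, but the documents do not support this: naming ANOVA excludes no covariate, and the SAP, which is not in the supplied text, may already contain one.

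A reader might also infer that ANOVA is wrong or biased here. It is neither. Treatment is randomised, and omitting a baseline term costs at most precision.

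Three further objections limit the size of the gain, and all stand:
- The lower end is not secure. Modest changes in the assumed score distribution bring the correlation down to break-even, so a guaranteed gain cannot be claimed. Higher assumed means would raise it, so the range is open in both directions.
- Allergen is titrated at Visit 2 to a positive reaction. This could compress the spread at Visit 3 beyond the entry cut, and it is not modelled. In the other direction, criterion 10 needs a score of 2 or more at only two of three time points, so the restriction on a single-minute score may be milder than simulated.
- Section 20.5.1 lists 2 measures × 3 minutes × 3 visits = 18 comparisons. The power figures describe one of them and not the trial's overall conclusion.

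**Conclusion.** The point holds as an optional improvement. The supplied text names ANOVA, commits to no baseline term, and shows that both primary measures are scored post-challenge before randomisation. Using that score would probably help a little: power for one comparison moves from 63.7% to about 64–69%, against a loss of about 1.2 points if the score predicts nothing.

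These figures rest on an assumed difference of 0.75 SD and assumed observed correlations of about 0.16 to 0.37, neither of which is in the documents. A larger benefit is tempting to quote, but 11 points would need an observed correlation of 0.5, and nothing in the documents supports one that high after the entry selection.

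**What to change.** In the SAP due before database lock, specify the following, or confirm it if already there:
- Each primary endpoint is analysed by ANCOVA, with treatment as factor and the Visit 3 post-challenge score of the same measure as covariate.
- The two eyes are combined for the covariate by the same rule as for the outcome, and that rule is stated. Reactions are assessed in both eyes and product "will be administered bilaterally into the eye", but the supplied text gives no combining rule.
- For an outcome at one minute, the covariate is the Visit 3 score at that minute, or the mean of the Visit 3 time points if that minute was not scored then. For a visit mean, it is the Visit 3 mean.
- Unadjusted ANOVA is reported as a sensitivity analysis.

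Extend this to a secondary measure only if it was scored at Visit 3.

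The cost is one paragraph, one degree of freedom and no new data for itching and redness. Section 20.3 provides that "Any changes in the statistical methods described in this protocol that occur prior to database lock will be documented in the SAP", without a protocol amendment.
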